APPENDIX 6: ECOG PERFORMANCE STATUS CRITERIA

ECOG Performance Status Scale	
Grade	Descriptions
0	Normal activity. Fully active, able to carry on all pre-disease performance without restriction.
1	Symptoms, but ambulatory. Restricted in physically strenuous activity, but ambulatory and able to carry out work of a light or sedentary nature (e.g., light housework, office work).
2	In bed <50% of the time. Ambulatory and capable of all self-care, but unable to carry out any work activities. Up and about more than 50% of waking hours.
3	In bed >50% of the time. Capable of only limited self-care, confined to bed or chair more than 50% of waking hours.
4	100% bedridden. Completely disabled. Cannot carry on any self-care. Totally confined to bed or chair.
5	Dead

APPENDIX 7: RECIST CRITERIA VERSION 1.1

Response Evaluation Criteria in Solid Tumors (RECIST) Quick Reference

ELIGIBILITY

Only subjects with measurable or evaluable disease at baseline should be included in protocols where objective tumor response is the primary endpoint.

Measurable Disease – the presence of at least one measurable lesion. If the measurable disease is restricted to a solitary lesion, its neoplastic nature should be confirmed by cytology/histology.

Measurable Lesions – lesions that can be accurately measured in at least one dimension with the minimum size of:

- 10 mm by CT scan or MRI (no less than double the slice thickness and a minimum of 10 mm).
- 10 mm caliper measurement by clinical exam (lesions which cannot be accurately measured with calipers should be recorded as non-measurable).
- 15 mm for nodal disease in short axis
- 20 mm by chest X-ray (if clearly defined and surrounded by aerated lung)
- Malignant lymph node: 15 mm in short axis when assessed by CT scan (CT scan slice thickness no greater than 5 mm). At baseline and in follow-up only the short axis is to be followed.

Non-Measurable Lesions – all other lesions, including small lesions (longest diameter <10 mm or pathological lymph nodes with ≥ 10 to <15 mm short axis) as well as truly non-measurable lesions. Lesions considered truly non-measurable include leptomeningeal disease, ascites, pleural/pericardial effusion, inflammatory breast disease, lymphangitic involvement of skin or lung, abdominal masses/abdominal organomegaly identified by physical examination that is not measurable by reproducible imaging techniques, and nodal disease that is 10 to <15 mm in short axis.

Special Considerations Regarding Lesion Measurability: Bone lesions, cystic lesions, and lesions previously treated with local therapy require particular comment:

Bone lesions:

- Bone scan, PET scan or plain films are not considered adequate imaging techniques to measure bone lesions. However, these techniques can be used to confirm the presence or disappearance of bone lesions.
- Lytic bone lesions or mixed lytic-blastic lesions, with identifiable soft tissue components, that can be evaluated by cross sectional imaging techniques such as CT or MRI can be considered as measurable lesions if the soft tissue component meets the definition of measurability described above.
- Blastic bone lesions are non-measurable.

Cystic lesions:

- Lesions that meet the criteria for radiographically defined simple cysts should not be considered as malignant lesions (neither measurable nor non-measurable) since they are, by definition, simple cysts.
- 'Cystic lesions' thought to represent cystic metastases can be considered as measurable lesions, if they meet the definition of measurability described above. However, if noncystic lesions are present in the same subject, these are preferred for selection as target lesions.

Lesions with prior local treatment:

- Tumor lesions situated in a previously irradiated area, or in an area subjected to other loco-regional therapy, are usually not considered measurable unless there has been demonstrated progression in the lesion. Study protocols should detail the conditions under which such lesions would be considered measurable.

Measurement of Lesions

- All measurements should be taken and recorded in metric notation, using calipers if clinically assessed. All baseline evaluations should be performed as closely as possible to the beginning of treatment and never more than 28 days before the beginning of the treatment.

Methods of Measurement

- The same method of assessment and the same technique should be used to characterize each identified and reported lesion at baseline and at each subsequent response assessment. Imaging based evaluation should always be done rather than clinical examination unless the lesion(s) being followed cannot be imaged but are assessable by clinical examination.
- For the case of skin lesions, documentation by color photography, including a ruler to estimate the size of the lesion, is recommended.
- CT is currently the best currently available and reproducible method to measure target lesions selected for response assessment. The CT scan slice thickness should be 5 mm or less. When the CT scans have a slice thickness that is greater than 5 mm, the minimum size for a measurable lesion should be twice the slice thickness. MRI is also acceptable.
- Lesions on chest X-ray are acceptable as measurable lesions when they are clearly defined and surrounded by aerated lung. However, CT is preferable.
- Ultrasound (US) should not be used to measure tumor lesions. The utilization of endoscopy and laparoscopy for objective tumor evaluations not advised.
- Fluorodeoxyglucose positron emission tomography (FDG-PET) can be used to determine a new lesion if the lesion was absent at baseline on FDG-PET
- Tumor markers alone cannot be used to assess response. If markers are initially above the upper normal limit, they must normalize for a subject to be considered in complete response when all lesions have disappeared.
- Cytology and histology can be used to differentiate between PR and CR in rare cases (eg, after treatment to differentiate between residual benign lesions and residual malignant lesions in tumor types such as germ cell tumors).

Baseline Documentation of “Target” and “Non-Target” Lesions

- All measurable lesions up to a maximum of two lesions per organ and 5 lesions in total, representative of all involved organs should be identified as **target lesions** and recorded and measured at baseline.
- Target lesions should be selected on the basis of their size (lesions with the longest diameter [LD]) and be representative of all involved organs, but in addition should lend themselves accurate repeated measurements.
- A sum of the LD for all target lesions will be calculated and reported as the baseline sum diameters. The baseline sum diameters will be used as reference by which to characterize the objective tumor. If lymph nodes are to be included in the sum, then as noted above, only the short axis is added to the sum.
- If a target lesion becomes too small to measure, a default value of 5 mm is assigned. If the lesion disappears, the measurement is recorded at 0 mm.
- If extranodal target lesions fragment, the LDs of the fragmented portions are added in the sum. If targets lesions coalesce and cannot be distinguished, the LD of the coalesced lesion is added to the sum.
- For a subject with SD or PR, a lesion which disappears and then reappears will continue to be measured and added to the sum. Response will depend upon the status of the other lesions. For a subject with CR, reappearance of a lesion is considered PD.
- New lesions should be unequivocal and not attributable to differences in scanning technique or findings which may not be tumor. If a new lesion is equivocal, repeat scans are needed to confirm. If confirmed, PD is assessed from the date of the first scan.
- All other lesions (or sites of disease) should be identified as **non-target lesions** and should also be recorded at baseline. Measurements of these lesions are not required, but the presence or absence of each or in rare case unequivocal progression should be noted at each subsequent response assessment.

RESPONSE CRITERIA

Evaluation of Target Lesions

Complete Response (CR):	Disappearance of all target lesions. Any pathological lymph node (whether target or nontarget) must have reduction in short axis to <10 mm
Partial Response (PR):	At least a 30% decrease in the sum of the diameters of target lesions, taking as reference the baseline sum diameters
Progressive Disease (PD):	At least a 20% increase in the sum of the diameters of target lesions, taking as reference the smallest sum on study (this includes the baseline sum if that is the smallest on study). In addition to the relative increase of 20%, the sum must also demonstrate an absolute increase of at least 5 mm. The appearance of one or more new lesions is also considered progression.

Evaluation of Non-Target Lesions

Complete Response (CR):	Disappearance of all non-target lesions and normalization of tumor marker level. All lymph nodes must be non-pathological in size (ie, <10 mm short axis).
Non-CR/Non-PD	Persistence of one or more non-target lesion(s) and/or maintenance of tumor marker level above the normal limits
Progressive Disease (PD):	Unequivocal progression of the existing non-target lesions. The appearance of one or more new lesions is also considered progressive disease.

Although a clear progression of “non target” lesions only is exceptional, in such circumstances, the opinion of the investigator should prevail.

Evaluation of Overall Response

Table 6 Evaluation of Overall Response

Target lesions	Non-Target lesions	New Lesions	Overall response
CR	CR	No	CR
CR	Non-CR/Non-PD	No	PR
CR	Not evaluated	No	PR
PR	Non-PD or not all evaluated	No	PR
SD	Non-PD or not all evaluated	No	SD
Not all evaluated	Non-PD	No	NE
PD	Any	Yes or No	PD
Any	PD	Yes or No	PD
Any	Any	Yes	PD

- Subjects with a global deterioration of health status requiring discontinuation of treatment without objective evidence of disease progression at that time should be classified as having “symptomatic deterioration”. Every effort should be made to document the objective progression even after discontinuation of treatment.
- In some circumstances it may be difficult to distinguish residual disease from normal tissue. When the evaluation of complete response depends on this determination, it is recommended that the residual lesion be investigated (fine needle aspirate/biopsy) to confirm the complete response status. If described in the clinical protocol, FDG-PET may be used to upgrade a response to a CR in a manner similar to a biopsy in cases where a residual radiographic abnormality is thought to represent fibrosis or scarring

REPORTING OF RESULTS

All subjects included in the study must be assessed for response to treatment, even if there are major protocol treatment deviations or if they are ineligible. Each subject will be assigned one of the following categories: 1) complete response, 2) partial response, 3) stable disease, 4) progressive disease, 5) not evaluable for response: specify reason such as early death from malignant disease, early death from toxicity, tumor assessments not repeated/incomplete, or other (specify).

RECIST 1.1 and iRECIST

	RECIST 1.1	iRECIST
Definitions of measurable and non-measurable disease; numbers and site of target disease	Measurable lesions are 10 mm or more in long diameter (15 mm for nodal lesions); maximum of 5 lesions (2 per organ); all other disease considered not target (must be 10 mm or longer in short axis for nodal disease)	No change; however, NEW lesions are evaluated as per RECIST 1.1 but are recorded separately on the CRF (but not included in the sum of lesions for target lesions identified at baseline)
R, PR or SD	Cannot have met criteria for PD prior to CR, PR or SD	May have had iUPD (1 or more instances), but not iCPD, prior to iCR, iPR or iSD
Confirmation of CR, PR	Only required for non-randomised trials	As per RECIST 1.1
Confirmation of SD	Not required	As per RECIST 1.1
New lesions	Results in PD. Recorded but not measured	Results in iUPD but iCPD is only assigned based on this category if at next assessment 
 Additional NL appear or Increase in size of NLs (≥ 5 mm for sum of NLT or any increase in NLNT) NLs, where none have previously been recorded can also confirm iCPD
Independent blinded review and central collection of scans	Recommended in some circumstances	Collection of scans (but not independent review) recommended for all trials
Confirmation of PD	Not required (unless equivocal)	Required
Consideration of clinical status	Not included in assessment	Clinical stability (see definition) is considered in whether treatment is continued after iUPD

NT = non-target, T = target; NL = new lesions; NLT = new lesion target; NLNT = new lesion non target; iUPD = unconfirmed immune PD; iCPD = confirmed immune PD; SOM= sum of measures. iCR = immune complete response; iPR = immune partial response; iSD = immune stable disease

Assigning time-point response for iRECIST

Time-point response				
Target Lesions*	Non-Target Lesions*	New Lesions*	Time Point Response	
			No prior iUPD**	Prior iUPD**; ***
iCR	iCR	No	iCR	iCR
iCR	Non-iCR/Non-iUPD	No	iPR	iPR
iPR	Non-iCR/Non-iUPD	No	iPR	iPR
iSD	Non-iCR/Non-iUPD	No	iSD	iSD
iUPD with no change OR decrease from last TP	iUPD with no change OR decrease from last TP	Yes	NA	NLs confirms iCPD if NLs were previously identified and increase in size (≥ 5 mm in SOM for NLT or any increase for NLNT) or number; If no change in NLs (size or number) from last TP, remains iUPD
iSD, iPR, iCR	iUPD	No	iUPD	Remains iUPD unless iCPD confirmed based in further increase in size of NT disease (need not meet RECIST 1.1 criteria for unequivocal PD)
iUPD	Non-iCR/Non-iUPD; iCR	No	iUPD	Remains iUPD unless iCPD confirmed based on: 
 • further increase in SOM of at least 5 mm, otherwise remains iUPD
iUPD	iUPD	No	iUPD	Remains iUPD unless iCPD confirmed based on further increase in: 
 • previously identified T lesion iUPD in SOM ≥ 5 mm and / or • NT lesion iUPD (prior assessment - need not be unequivocal PD)
iUPD	iUPD	Yes	iUPD	Remains iUPD unless iCPD confirmed based on further increase in: 
 • previously identified T lesion iUPD SOM ≥ 5 mm and / or • previously identified NT lesion iUPD (need not be unequivocal) and /or • size or number of new lesions previously identified
Non-iUPD/PD	Non-iUPD/PD	Yes	iUPD	Remains iUPD unless iCPD confirmed based on 
 • increase in size or number of new lesions previously identified

* Using RECIST 1.1 principles. If no PSPD occurs, RECIST 1.1 and iRECIST categories for CR, PR and SD would be the same. ** in any lesion category. *** previously identified in assessment immediately prior to this TP.

iCR = immune complete response; iPR = immune partial response; iSD = immune stable disease; iUPD = immune unconfirmed progression; iCPD = immune confirmed progression; NL = new lesion; NLT = new lesion target; NLNT = new lesion non target; T = target; TP = timepoint; NA = not applicable; NE = not evaluable / evaluated

Assigning best overall response for iRECIST

Best overall response					
TPR1	TPR2	TPR3	TPR4	TPR5	iBOR
iCR	iCR, iPR, iUPD, NE	iCR, iPR, iUPD, NE	iUPD	iCPD	iCR
iUPD	iPR, iSD, NE	iCR	iCR, iUPD, NE	iCR, iPR, iSD, iUPD, iCPD, NE	iCR
iUPD	iPR	iPR, iSD, iUPD, NE	PR, iSD, iUPD, NE, iCPD	iPR, iSD, iUPD, NE, iCPD	iPR
iUPD	iSD, NE	iPR	iPR, iSD, iUPD, NE	PR, iSD, iUPD, iCPD, NE	iPR
iUPD	iSD	iSD, iUPD, NE	iSD, iUPD, iCPD, NE	iSD, iUPD, iCPD, NE	
iUPD	iCPD	Anything	Anything	Anything	iCPD
iUPD	iUPD (no iCPD)	iCPD	Anything	Anything	iCPD
iUPD	NE	NE	NE	NE	iUPD

Examples only – many more scenarios exist but follow the same principles
Table assumes a randomised study where confirmation of CR or PR is not required
For patients with non-target disease only at baseline, only iCR or non-CR/non-PD can be assigned at each TPR but is not shown in the table for ease of presentation

iCR = immune complete response; iPR = immune partial response; iSD = immune stable disease; iUPD = immune unconfirmed progression; iCPD = immune confirmed progression; NL = new lesion; NLT = new lesion target; NLNT = new lesion non target; T = target; TP = timepoint; NA = not applicable; NE = not evaluable / evaluated

Source:

As part of paper presented at the EORTC-NCI-AACR 2016 Meeting (Munich)

Later published as part of Seymour, L., et al., iRECIST: guidelines for response criteria for use in trials testing immunotherapeutics. Lancet Oncol, 2017. Mar; 18(3): e143-e152.

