6. RESPONSE ASSESSMENTS

6.1. Radiographic Evaluations and Confirmation of Disease Progression

Response and progression will be determined by investigator assessment of on-trial radiographic evaluations, that will be conducted every 8 (± 1) weeks through Week 48 and then at least every 12 (± 1) weeks until confirmed progression of disease (as defined below), alternate anticancer therapy, withdrawal of consent, or death, whichever occurs first. The radiographic assessments are to be conducted as noted, independent of dose delays and/or dose interruptions. RECIST 1.1 criteria will be used for primary endpoint evaluation (Eisenhauer et al., 2009), iRECIST will be used for exploratory endpoint response evaluation (Seymour et al., 2017).

Radiographic evaluation may be done using either CT or MRI, but the modality chosen to evaluate each individual subject should be the same as the screening evaluation throughout the duration of the study.

Under specific circumstances subjects who develop PD per RECIST v1.1 may continue treatment and be followed for improved response or confirmed progression of disease [treatment beyond progression (Section 6.2)]. Regardless of whether or not a subject continues treatment in the event of RECIST-determined PD, follow-up radiographic assessments to confirm progression or show improvement in response are to be conducted at least 4 weeks after the assessment of PD per RECIST v1.1 (unless there is prior clinical deterioration, initiation of other cancer therapy, or withdrawal of consent).

For subjects who continue treatment beyond progression (Section 6.2), iRECIST PD should be confirmed at least 4 to 8 weeks after the first radiologic evidence of PD in clinically stable participants.

Subjects who have unconfirmed PD (iUPD) may continue study treatment until progression is confirmed as long as the subject is clinically stable and has provided written informed consent prior to receiving additional treatment (Section 6.2). Clinically unstable subjects should be discontinued from study treatment at the first occurrence of radiographic PD (iUPD) and are not required to have repeat imaging to confirm PD by iRECIST (though a confirmation of progression scan may be obtained at the investigator's discretion after consultation with the sponsor).

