If repeat imaging shows iRECIST confirmed disease progression (iCPD), subjects will discontinue treatment. However, if the subject is deriving benefit after iCPD is observed, an exception to continue study treatment must be approved by the sponsor's Medical Monitor. Subjects who have repeat imaging to confirm progression are not required to undergo the next scheduled tumor imaging if it is less than 4 weeks later.

If repeat imaging shows iRECIST stable disease (iSD), iRECIST partial response (iPR), or iRECIST complete response (iCR), imaging should be continued every 8 (± 1) weeks and the subject should continue on trial treatment.

Note that the date of progression to be used for all relevant efficacy endpoints will be based on first documentation of PD (ie, RECIST v1.1 date of PD), regardless of date of confirmation of PD for subjects who continue on treatment.

All radiographic evaluations performed on the study will be collected and held for a potential independent review. Details regarding initiating an independent review will be outlined in the statistical analysis plan (SAP).

Confirmed progression of disease is defined as one of the following:

Clinical deterioration with or without radiographic PD per RECIST v1.1 (See [Appendix 7](#)) will confirm progression of disease. Note, however, that radiographic evaluation should be conducted at the time of clinical signs and/or symptoms of PD whenever possible.

- In subjects without clinical deterioration at the time of a radiographic scan showing PD per RECIST v1.1, a second scan conducted at least 4 weeks later showing progression of disease as outlined below will confirm progression:
- An additional 10% increase in tumor burden with a minimum 5 mm absolute increase from time of initial PD. This includes an increase in the sum of diameters of all target lesions and/ or the diameters of new measurable lesions compared to the time of initial PD.

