8.2. Efficacy Assessments

Planned timepoints for all efficacy assessments are provided in the SoA.

Screening and subsequent tumor assessments must include CT scans (with IV contrast unless contraindicated and oral contrast as appropriate per institutional standards) of the head and neck, chest, abdomen, pelvis and other site of disease for sarcoma as needed. If a CT scan for tumor assessment is performed in a positron emission tomography (PET)/CT scanner, the CT acquisition must be consistent with the standards for a full-contrast CT scan. Brain imaging (either MRI or contrast-enhanced CT) is required at screening for all subjects. Further investigations such as bone scans and CT scans of the neck should also be performed if there is any clinical suspicion of disease at any site that may not be demonstrated by the minimum schedule of assessments listed above. At the investigator's discretion, other methods of assessment of measurable disease as per RECIST v1.1 may be used.

The same radiographic procedures used to assess disease sites at screening should be used throughout the study (eg, the same contrast protocol for CT scans). Response will be assessed by the investigator on the basis of physical examinations and the imaging modalities detailed above, using RECIST criteria. Assessments should be performed by the same evaluator, if possible, to ensure internal consistency across visits.

Tumor assessments will be performed every 8 (± 1) weeks from Cycle 1 Day 1 through Week 48 and then at least every 12 (± 1) weeks or as clinically indicated until confirmed progression of disease (as defined below), alternate anticancer therapy, withdrawal of consent, or death, whichever occurs first. The radiographic assessments are to be conducted as noted, independent of dose delays and/or dose interruptions. RECIST 1.1 criteria will be used for primary endpoint evaluation ([Eisenhauer et al., 2009](#)), iRECIST will be used for exploratory endpoint response evaluation ([Seymour et al., 2017](#)).

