10.8.3.2. Duration of Response (iRECIST)

Duration of response (DoR) is defined as the time, in days, from the first of the 2 assessments required for confirmed iPR or iCR to the time of the iCPD or death due to underlying cancer.

The duration will be calculated (in days) as:

Date of first overall response of iCPD or date of death due to underlying cancer (whichever is first) – Date of first of the two assessments required for confirmed iCR or iPR.

The duration of response will be summarised by cohort using descriptive summaries, which will not account for censoring. Additionally, Kaplan-Meier curves will be produced for each cohort along with a table summarising the median and 25th and 75th percentiles of the duration of response, inclusive of censoring, for each cohort, including sub-cohort.

[Kaplan-Meier plot: y-axis = cumulative proportion of participants who still have response, x-axis = day, one line for each cohort, including sub-cohort, overlayed on the same plot].

Exclusion

If a subject does not achieve confirmed iCR or iPR they will be excluded from this analysis.

Censoring

If a subject does not experience iCPD or death due to underlying cancer their duration will be censored at the date of their last disease assessment.

If a subject dies due to a cause other than underlying cancer they will be censored at the date of death.

If a subject does not have a disease assessment after their assessment confirming their response as iCR or iPR they will be censored at the date of their last disease assessment.

If a subject initiates another cancer treatment prior to iCPD/death their duration of response will be censored at the last assessment prior to initiation of the alternative cancer treatment.

If a subject experiences iCPD or death immediately following 2 or more visits at which their response was missing or NE their duration of response will be censored at the time of their last assessment prior to missing/NE response.

10.8.3.3. *Progression Free Survival (RECIST)*

Progression-free survival (PFS) is defined as the time, in days, from the first date of treatment until the first date at which PD is experienced or the subject dies due to any cause. Only deaths that occur within 30 days of the last tumor assessment will be included.

The duration will be calculated (in days) as:

Date of first overall response of PD or date of death due to any cause (whichever is first) – Date of first treatment.

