Progression-free survival will be summarised by cohort, and sub-cohort for cohort F, using descriptive summaries, which will not account for censoring. Additionally, Kaplan-Meier curves will be produced for each cohort, and sub-cohort for cohort F, along with a table summarising the median and 25th and 75th percentiles of the progression-free survival, inclusive of censoring, for each cohort, including sub-cohort.

[Kaplan-Meier plot: y-axis = cumulative proportion of participants who are progression free, x-axis = day, one line for each cohort, including sub-cohort, overlayed on the same plot].

Censoring

If a subject does not experience PD or death they will be censored at the date of their last disease assessment.

If a subject does not have a disease assessment after their first treatment they will be censored at the date of their first treatment.

If a subject initiates another cancer treatment prior to PD/death they will be censored at the last assessment prior to initiation of the alternative cancer treatment.

If a subject experiences PD or death immediately following 2 or more visits at which their response was missing or NE they will be censored at the time of their last assessment prior to missing/NE response.

10.8.3.4. *Progression Free Survival (iRECIST)*

Progression-free survival (iPFS) is defined as the time, in days, from the first date of treatment until the first date at which iCPD is experienced or the subject dies due to any cause. Only deaths that occur within 30 days of the last tumor assessment will be included.

The duration will be calculated (in days) as:

Date of first overall response of iCPD or date of death due to any cause (whichever is first) – Date of first treatment.

Progression-free survival will be summarised by cohort, and sub-cohort for cohort F, using descriptive summaries, which will not account for censoring. Additionally, Kaplan-Meier curves will be produced for each cohort, and sub-cohort for cohort F, along with a table summarising the median and 25th and 75th percentiles of the progression-free survival, inclusive of censoring, for each cohort, including sub-cohort.

[Kaplan-Meier plot: y-axis = cumulative proportion of participants who are progression free, x-axis = day, one line for each cohort, including sub-cohort, overlayed on the same plot].

Censoring

If a subject does not experience iCPD or death they will be censored at the date of their last disease assessment.

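### Protocol Section 6.1 and Appendix 7 conflict on clinical deterioration without a PD scan, and the SAP's default handling tends to raise Kaplan-Meier PFS, DoR and DoSD

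*Protocol*

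**What the plan says.** **Protocol Section 6.1.** "Clinical deterioration with or without radiographic PD per RECIST v1.1" is said to confirm progression. The next sentence asks that "radiographic evaluation should be conducted at the time of clinical signs and/or symptoms of PD whenever possible". Scheduled imaging in Sections 6.1 and 8.2 runs "until confirmed progression of disease (as defined below), alternate anticancer therapy, withdrawal of consent, or death, whichever occurs first". Sections 4.2 and 6.1 keep scans going for subjects who stop treatment before confirmed progression. Section 6.1 also dates progression, for efficacy endpoints, by the first RECIST v1.1 PD.

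**Protocol Appendix 7.** It describes the same course in these words: "global deterioration of health status requiring discontinuation of treatment without objective evidence of disease progression at that time should be classified as having"; the label it then gives is symptomatic deterioration. It adds: "Every effort should be made to document the objective progression even after discontinuation of treatment". PD is defined there only by lesion growth or new lesions, and the RECIST 1.1 column of its comparison table leaves clinical status out of the assessment.

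**Other protocol passages.** Section 8.2 and the tumor-assessment note to the Section 8.1 schedule call for a response assessment at treatment termination, unless one was done in the previous 14 days or PD is already documented. Section 7 asks that assessments continue while there is no progressive disease and no new therapy.

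**SAP.** Endpoints use the response recorded in the database (10.8.1.1). PFS (10.8.3.3) counts a recorded PD, or a death within 30 days of the last tumor assessment. Otherwise: "If a subject does not experience PD or death they will be censored at the date of their last disease assessment". DoR (10.8.2.2) and DoSD (10.8.2.3) count a recorded PD or death from the underlying cancer, with no 30-day limit, and censor at the last assessment if there is neither. No rule covers clinical progression without a PD scan.

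**The concern.** The protocol gives one clinical course two labels. Under Section 6.1 the subject has confirmed progression and scheduled scans end. Under Appendix 7 the subject has no RECIST PD and objective progression should still be sought. The SAP looks only for a recorded PD or a qualifying death, so the outcome depends on whether a further scan is done and on which passage the site follows.

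A subject left with no PD record is censored because the disease appears to be failing. That is informative censoring. Kaplan-Meier assumes that those censored would have fared like those still under observation, so the curve tends to be too high. DoR and DoSD are secondary endpoints, PFS is exploratory, and Section 1.4.1 says that ORR together with DoR is meant to inform later studies.

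**Working it through.** **1. The plan's own figures.** The only design figures are for ORR. For a Simon design, the probability of rejecting is the sum, over stage 1 counts x that allow continuation, of P(X1 = x) × P(X2 ≥ r − x), where r is the number of responders needed in 29.
- Type 1 (10 then 19; continue if ≥1; r = 4): 0.0468 at a rate of 0.05 and 0.8011 at 0.2.
- Type 2 (continue if ≥2; r = 6): 0.0471 at 0.1 and 0.8051 at 0.3.

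All four agree with the plan. None involves PFS, DoR or DoSD.

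**2. One subject traced.** Stable disease at week 8, clinical deterioration at week 13. The gap is 5 × 7 = 35 days, so:
- if no further scan is done, PFS is censored at week 8, and no later death can count because 35 > 30;
- a termination scan is due under Section 8.2, because 35 > 14 and no PD is documented. If it shows PD, there is an event; if not, the censoring date and the 30-day window move later.

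**3. Size for 6-month PFS with no further scan (illustration).** Assumptions: exponential progression with 25% event-free at 6 months (182 days), the combination-arm figure in Protocol Section 1.2; scans every 56 days; a share f of progressions after the first scan is clinical only; deaths ignored.

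Rate λ = ln 4/182. Per scan interval, s = exp(−56λ) = 0.6528 and p = 1 − s = 0.3472. Three scans (days 56, 112, 168) fall before day 182.

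Deterioration counted as an event on its date: S = 0.25 + (1 − f)(s³ − 0.25), with s³ = 0.2781.

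Censored at the last scan: each interval after the first has at-risk fraction 1 − fp and event fraction (1 − f)p, so S = s³/(1 − fp)².

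| f | Event on date | Censored | Difference (points) |
|---|---|---|---|
| 10% | 27.5% | 0.2781/0.9653² = 29.9% | 2.3 |
| 20% | 27.3% | 0.2781/0.9306² = 32.1% | 4.9 |
| 30% | 27.0% | 0.2781/0.8958² = 34.7% | 7.7 |

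Differences are taken before rounding. A simulation of 60,000 subjects gives 29.7/32.0/34.6% against 27.4/27.1/26.8%.

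**4. With a termination scan.** Same model, simulated with 400,000 subjects. Each clinical-only subject is scanned 14 days after deterioration; the scan shows PD in 50% or 75% (assumed), and the rest are censored at that scan.

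| f | 50% show PD | 75% show PD | Difference from event on date |
|---|---|---|---|
| 10% | 28.9% | 28.3% | 1.4 / 0.8 |
| 20% | 30.0% | 28.9% | 2.7 / 1.6 |
| 30% | 31.3% | 29.5% | 4.3 / 2.5 |

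**5. DoSD.** A second simulation applied the SAP death and censoring rules: true median 112 days, 20% clinical only (here from first dose), median 60 days from progression to death, no further scan. At day 113:
- event counted: 0.499;
- PFS under the SAP: 0.558;
- DoSD under the SAP: 0.544 if no one starts new therapy, 0.565 if all do.

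DoR was not simulated. Its event and censoring rules are nearly the same, but it covers confirmed responders only.

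**6. Summaries that ignore censoring.** In the same scenario, if censored times are used as durations, mean PFS is 180 days under the SAP, against 185 (event on date) to 191 (PD at the next scan). The direction reverses.

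**The case against.** The strongest reply is that the protocol does ask for the missing scan: at deterioration where possible, at termination, and afterwards while there is no PD. Censoring at week 8 is then the missed-scan case, not what the plan prescribes. Event dating also looks settled. Section 6.1 uses the RECIST v1.1 date, SAP Table 5 offers no clinical route to PD, and confirmed progression mainly governs stopping treatment. A site entering PD on clinical grounds would be misreading the plan, and nothing shows that this happened.

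Much of this stands, and it is why step 4 is needed. It does not remove the problem. No passage says whether the termination and follow-up scans apply once Section 6.1 has declared progression, and the subjects least able to be scanned are those at issue. Dating progression by a RECIST PD gives no event where no scan shows PD.

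A reader might infer more than the documents support:
- that Appendix 7 makes further imaging mandatory: it says effort should be made;
- that the SAP censors these subjects for all three endpoints: DoR and DoSD count a later cancer death, so the event may be late rather than lost;
- that the durations are shown to be overstated: the clinical-only share is assumed, the 25% anchor comes from a 10-subject arm (95% CI 3.7 to 55.8), and uncensored summaries can move the other way.

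**Conclusion.** The conflict is in the text, and the SAP has no rule that resolves it. Where no later scan records PD, PFS is censored informatively, and DoR and DoSD are counted late or censored. The likely direction for Kaplan-Meier estimates is upward.

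If 10–30% of progressions after the first scan are clinical only, 6-month PFS rises by about 2 to 8 points with no further scan, and by roughly 1 to 4 points if a termination scan shows PD in 50–75% of them. Both ranges rest on exponential progression, the 25% anchor and an assumed share.

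It would be wrong to read this as a threat to the primary result: ORR, the Simon rules and the stated error rates and power do not change, and the SAP plans no hypothesis tests. The point is worth correcting because it bears on two secondary endpoints and the correction is cheap.

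**What to change.** **Protocol.** Reconcile Sections 6.1 and 8.2 with Appendix 7, and with Section 7 and the termination-scan rule in Sections 8.1 and 8.2. State whether imaging continues after clinical deterioration without radiographic PD, and whether such deterioration may be entered as a RECIST response of PD. This concerns assessment and recording only; no treatment rule is proposed.

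**SAP 10.8.2.2, 10.8.2.3 and 10.8.3.3.** Add a sensitivity analysis that counts discontinuation for clinical progression or symptomatic deterioration as an event on that date, printed beside the RECIST-only estimate. Report the number of such subjects by cohort, so that the share assumed above is replaced by an observed one.

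**Cost.** One extra row per endpoint, with somewhat shorter durations in that row. Identifying the subjects relies on the withdrawal reason (Listing 16.2.1.1) and progression date (Listing 16.2.1.2). Neither shell has a field separating clinical from radiographic progression, so cases should be checked against the scan records at the data review meeting. SAP 6.3 records that the study was terminated, so new protocol wording can recover few scans; the SAP change is the part that still helps.
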